10.0 Confidentiality, Privacy and Data Management

See the Research Data Plan Review Form

11.0 Data and Safety Monitoring Plan – N/A

12.0 Risks

- Loss of confidentiality – This will be minimized by the appropriate selection of study subjects, access to research records limited to HMC research personnel, compliance with HMC research data and integrity policy, and the use of a study ID code to label all data and specimens .
- Risk of randomization - Participants will be assigned to a treatment program by chance. The treatment received may prove to be less effective or to have more side effects than the other research treatment(s) or other available treatments.
- Risk associated with removing blood by venipuncture is a slight pinch or pin prick when the sterile needle enters the skin. The risks include mild discomfort and/or a black and blue mark at the site of puncture. Less common risks include a small blood clot, infection or bleeding at the puncture site, and on rare occasions fainting during the procedure.
- Risk of injury to participant when conducting upper body exercises. Participants will be provided written instructions on how to perform their upper body exercises at home (using a chair) in order to minimize risk of injury.

13.0 Potential Benefits to Subjects and Others

13.1 Potential Benefits to Subjects

Control Group – none

Intervention Group – minimize weight change

13.2 Potential Benefits to Others

This research may help in the education and treatment of future patients.

14.0 Sharing Results with Subjects – N/A

15.0 Economic Burden to Subjects

15.1 Costs

The albumin level and dietary scale will be provided at no cost to subjects. All other visits are standard of care.

15.2 Compensation for research-related injury

It is the policy of the institution to provide neither financial compensation nor free medical treatment for research-related injury. In the event of injury resulting from this research, medical treatment is available but will be provided at the usual charge. Costs for the treatment of research-related injuries will be charged to subjects or their insurance carriers.

16.0 Number of Subjects

See Section 9.

17.0 Resources Available

17.1 Facilities and locations

Penn State Milton S. Hershey Medical Center, Bone & Joint Institute.

17.2 Feasibility of recruiting the required number of subjects

Participants will be identified via their scheduled clinic visit with the research investigator.

17.3 PI Time devoted to conducting the research

Sufficient time will be devoted to conducting the research and reviewing the data.

17.4 Availability of medical or psychological resources – N/A

17.5 Process for informing Study Team

All team members will be given copies of all IRB approved documents – protocol, data collection tools, approval memos, etc. The team communicates regularly to review data and any updates.

18.0 Other Approvals

- Scientific Review Committee

19.0 Subject Stipend (Compensation) and/or Travel Reimbursements

N/A

20.0 Multi-Site Research

20.1 Communication Plans – N/A

20.2 Data Submission and Security Plan – N/A

20.3 Subject Enrollment – N/A

20.4 Reporting of Adverse Events and New Information – N/A

20.5 Audit and Monitoring Plans – N/A

21.0 Adverse Event Reporting

21.1 Reporting Adverse Reactions and Unanticipated Problems to the Responsible IRB

In accordance with applicable policies of The Pennsylvania State University Institutional Review Board (IRB), the investigator will report, to the IRB, any observed or reported harm (adverse event) experienced by a subject or other individual, which in the opinion of the investigator is determined to be (1) unexpected; and (2) probably related to the research procedures. Harms (adverse events) will be submitted to the IRB in accordance with the IRB policies and procedures

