3.3 Early Withdrawal of Subjects

3.3.1 Criteria for removal from study

Participants will be withdrawn from the study for safety reasons including severe adverse reactions, pregnancy, failure of subject to adhere to protocol requirements, or subject consent withdrawal.

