7.2.2 Visit 2 – Final Follow-Up Visit

Patients will return to the clinic site for their standard of care visit. At their final visit (when CAM boot use is no longer required), the following will occur:

- **Group 1 (Control):** Patient will be given an Albumin lab test request for blood (8mL) to be drawn at the PSHMC Clinical Laboratories at time of the final study visit. The blood draw

must occur within 5 days of the final visit. Final height and weight will be measured and recorded using a scale located in the practice site clinic.

- Group 2 (Intervention): Final height and weight will be measured and recorded using a scale located in the practice site clinic. Patient will be given an Albumin lab test request for blood (8mL) to be drawn at the PSHMC Clinical Laboratories at time of the final study visit. The blood draw must occur within 5 days of the final visit. Patient will complete the Participant Survey. The dietary scale is to be returned at this visit. Return of the Patient Diary is optional.

	Control	Intervention	
Visit 1 (Enrollment)	Albumin level (bloodwork)	Albumin level (bloodwork)	
	Weight	Weight	
	Height	Height	Patient Diary provided to patient
			Nutritional/Exercise Guidelines provided to patient
			Dietary Scale provided to patient
	Control	Intervention	
Visit 2 (Final Visit)	Albumin level (bloodwork)	Albumin level (bloodwork)	
	Weight	Weight	
	Height	Height	Participant Survey
			Dietary Scale returned
			Patient Diary returned (optional)

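### No systematic harm question is specified at the final visit in either arm, although exercise injury is a named risk of the intervention

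*Combined protocol and SAP*

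**What the plan says.** Section 12.0 lists four risks: loss of confidentiality, a generic risk of randomization, venipuncture, and "Risk of injury to participant when conducting upper body exercises". The last is the only specific risk tied to the intervention. The stated safeguard is a set of written instructions for exercising at home with a chair.

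Section 7.2.2 sets out the final visit. For both arms it gives albumin, and "Final height and weight will be measured and recorded using a scale located in the practice site clinic". For the intervention arm alone it adds return of the dietary scale, optional return of the diary, and a questionnaire: "Patient will complete the Participant Survey". The documents do not show what that questionnaire asks. Neither the text nor the visit table has an item on injury or other harm.

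Three other places bear on harm:

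- Section 3.3.1: "Participants will be withdrawn from the study for safety reasons including severe adverse reactions".
- Section 21.1 concerns "any observed or reported harm (adverse event) experienced by a subject or other individual". The investigator sends it to the IRB when, in the investigator's opinion, it is "1) unexpected; and (2) probably related to the research procedures".
- The safety monitoring entry reads "11.0 Data and Safety Monitoring Plan – N/A".

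The endpoints in Sections 1.2 and 1.3 are weight and albumin. Section 9.2 contains no safety analysis.

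**The concern.** The intervention arm is asked to exercise three days a week at home, with or without weights, between two study visits (Sections 7.2.1 and 7.3). The protocol foresees that someone may be hurt doing so, but it plans no occasion on which every patient is asked. What reaches the record then depends on who volunteers it.

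The trial is not blinded (Section 7.2.1), and only one arm is given exercises. Patients and staff may therefore be readier to mention, or to note, a strain in one arm than in the other. A difference in unsolicited reports could reflect prompting as easily as injury, and an absence of reports could reflect not asking. Answers that were never collected cannot be recovered at the analysis stage.

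Section 2.1 says the study is meant to inform providers about giving this information to patients placed in a boot. Readers of the result would want some account of harm beside the weight result.

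**Working it through.** **1. The passages side by side.**

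- Is a harm of the intervention foreseen? Yes, exercise injury (Section 12.0).
- Does any rule depend on harms being known? Yes, withdrawal after severe adverse reactions (Section 3.3.1).
- Is there a route by which harms come to notice? Yes: observed or reported (Section 21.1), at two visits in total (Section 7.3).
- Is there a question put to every patient in both arms? None is listed (Section 7.2.2, text and table).
- Could the Participant Survey serve? Possibly in the intervention arm, since its content is unseen. It is not given to controls, so it cannot give a like-for-like description of the two arms.
- Could the diary serve? It records meals and exercise, belongs to one arm, and is optional (Section 7.2.1).
- Is any tabulation of harm planned? None (Sections 1.2, 1.3 and 9.2).

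**2. The plan's own figure.** The protocol gives no injury rate and no calculation for harm. Its one power figure, 82% in Section 9.1, concerns weight. It reproduces: standardized difference 10/12 = 0.833; noncentrality 0.833 × √(25/2) = 2.95; a two-sided 0.05 t-test on 48 degrees of freedom gives 82.3% (83.8% by the normal approximation). Nothing below depends on it.

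**3. What one question would support if no injury is reported.** Input: 25 intervention patients (Section 9.1), all assumed to be asked and to answer. The exact binomial upper limit for 0 of n is 1 − a^(1/n).

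- Two-sided 95%: 1 − 0.025^(1/25) = 0.137, or 13.7%.
- One-sided 95%: 1 − 0.05^(1/25) = 0.113, or 11.3%.

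Without a question put to everyone there is no defined denominator, and no such limit can be stated.

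**4. The chance of seeing at least one injury among 25.** The formula is 1 − (1 − p)^25. The rates p are assumptions, because the documents give none.

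| Assumed true rate | Chance of at least one |
|---|---|
| 2% | 40% |
| 5% | 72% |
| 10% | 93% |
| 20% | 99.6% |

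A common injury would very probably show; a rare one might not.

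**5. Whether a formal comparison is worthwhile.** Two-sided Fisher exact test, 25 per arm, no events in controls: p = 2 × C(25, x)/C(50, x).

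- 5 against 0: 2 × 53,130/2,118,760 = 0.0502.
- 6 against 0: 2 × 177,100/15,890,700 = 0.022.

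About six events against none would be needed for p < 0.05, so description is the sensible aim.

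**The case against.** A reader might infer from these sections that harm cannot be detected at all. The documents do not support that. Section 21.1 covers harms that are observed or reported, Visit 2 is a clinic visit in person, and Section 3.3.1 acts on severe reactions that come to notice. Detection is possible; it is not systematic.

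A reader might also infer that the IRB rule shuts out exercise injury. A foreseen injury would ordinarily not count as unexpected, but the rule turns on the investigator's opinion, and an injury of surprising nature or severity could still qualify. The rule also limits what is sent to the IRB under institutional policy, not what may be asked or recorded.

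Nor do Sections 3.3.1 and 21.1 contradict each other. One concerns withdrawal after severe reactions, the other concerns which harms go to the IRB, and both can be followed together.

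The strongest remaining objection is that the gain is small. The exercises are seated and done to the patient's ability, and patients with vertigo or balance problems are excluded (Section 3.2). The protocol claims no safety conclusion and does not say it would recommend the programme on weight alone. Zero of 25 would still leave rates up to 13.7% compatible with the data. Controls are not given the exercises, so exercise injury as such has no control counterpart; only overall harm can be set side by side. The unseen survey might already ask the exposed arm about injury.

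All of this stands and limits the weight of the point. It does not supply a question asked alike in both arms.

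**Conclusion.** The point holds as an omission of modest weight. No systematic harm question is specified at the final visit in either arm, although the protocol names exercise injury as a risk and relies on severe reactions being known. Harm would probably be under-ascertained and could not be reliably described by arm.

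The gain from closing the gap is a descriptive count with a stated denominator. At best, 0 of 25 would bound the injury rate at 13.7% (two-sided) or 11.3% (one-sided). That assumes every intervention patient is enrolled as planned, reaches Visit 2 and answers; fewer answers would widen the limit. Under-ascertainment is a judgement from the absence of a listed question and the open-label design, not a measured quantity.

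The primary weight estimate, its power and its analysis are untouched. This is a cheap improvement, not a flaw in the main comparison.

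**What to change.** In Section 7.2.2 and the Visit 2 table, add for both arms the same short question, in the same words, about any injury, fall or other harm since Visit 1. Record every answer, whether or not the event is expected or thought related to the research.

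In Section 9.2, add one descriptive table: the number answering, and the number and percentage with any harm, by arm, with an exact confidence limit for the intervention arm. State that no formal test will be made. Showing the number answering matters because Section 3.3.2 ends data collection at withdrawal, so patients withdrawn earlier would not be reached by a Visit 2 question.

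Leave Section 21.1 unchanged. If the Participant Survey already asks about injury, say so and put the same item to the control arm.

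The cost is one extra form item and one table. No additional visit, test or patient is needed.

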21.2 Auditing and Inspecting

The investigator will permit study-related monitoring, audits, and inspections by the Penn State quality assurance program office(s), IRB, the sponsor, and government regulatory bodies, of all study related documents (e.g., source documents, regulatory documents, data collection instruments, study data etc.). The investigator will ensure the capability for inspections of applicable study-related facilities (e.g., pharmacy, diagnostic laboratory, etc.).

22.0 Study Monitoring, Auditing and Inspecting

22.1 Auditing and Inspecting

The investigator will permit study-related monitoring, audits, and inspections by the Penn State quality assurance program office(s), IRB, the sponsor, and government regulatory bodies, of all study related documents (e.g., source documents, regulatory documents, data collection instruments, study data etc.). The investigator will ensure the capability for inspections of applicable study-related facilities (e.g., pharmacy, diagnostic laboratory, etc.).

23.0 Reference – N/A

24.0 Appendix – N/A
